8.0 ADVERSE EVENT REPORTING

Adverse events are reported using two case report forms: Adverse Event and Serious Adverse Event. Adverse events will be collected starting at the time the patient is randomized and throughout the study, including during the hospital stay, any follow up visits and during any unscheduled patient contact or visits. The definitions and details are provided in the following sections.

Data Collection Requirements

Adverse Event Type	Adverse Event Form	Serious Adverse Event Form
Non-Serious Adverse Event	Complete entire form	DO NOT COMPLETE
Serious Adverse Event	DO NOT COMPLETE	Complete entire form

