6.3 Analysis population

Full Analysis Set (FAS): The set of subjects determined following the intent-totreat (ITT) principle refers to the data set constituted by all subjects who participate in the randomized study and receive the investigational product (implant) (i.e., ITT population defined in the protocol).

Per Protocol Set (PPS): Refers to the subgroup of treatment population who completes the trial and excluded the population that seriously violates the protocol (which means that study subjects violating the inclusion criteria or meeting exclusion criteria, loss to follow-up during the trial, cross enrollment, out-of-specification use of investigational products, out-of-window time, etc.).

Safety Set (SS): Set of all subjects who participate in the study and use the investigational products and undergo at least one safety evaluation after baseline. (The definitions of SS and FAS are the same. Therefore, SS is not defined separately).

Actual Treatment Set (ATS): All patients who participate in the randomized grouping, complete the trial, actually receive the scheduled treatment in the study (not necessarily consistent with the results of randomized grouping) and do not seriously violates the protocol. On the basis of PPS, only cross-enrolled patients are included, but they are then grouped and analyzed according to their actual treatment, i.e., the actual treatment set is formed.

The primary efficacy analysis will be based on FAS, PPS and ATS (if applicable). All baseline demographic data and secondary efficacy indicator analysis will be performed on the basis of FAS, and the safety evaluation will be performed on the basis of FAS.

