6.5 Missing values, abnormal values and outlying values

For possible missing data in the study process, the missing of primary efficacy endpoints will be carried forward only in principle during the analysis. LOCF (Last Observation Carry Forward) was used as sensitivity analysis for the missing of primary efficacy endpoints. That is, the last observed value is used to replace the missing value. In the sensitivity analysis of the LOCF, the last observed value is "Nonunion of fracture " unless the fracture union is definitive. Other missing indicators will not be carried forward and will be directly analyzed based on the actually observed data. Error and unreasonable data will be processed in the data cleaning process before statistical analysis. For withdrawal of subjects, this part of patient information will still be included in the final statistical analysis. Specific reasons for discontinuation or withdrawal of all patients will be explained in detail in the statistical report, and the missing primary endpoint due to early withdrawal will be analyzed according to the above strategy for processing missing values.

If the date (MMDDYYYY) of collection (non-CEC review data) during the trial is filled in with "UK" or "NA", no treatment will be done.

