7.4 Secondary endpoints

Secondary endpoints include the safety and effectiveness results, imaging outcomes and adverse events.

(1) Adverse events (type and frequency) for all adverse events will be compared for the study and control groups

Calculation principle: Based on the collected adverse events in the CRF, if the subject has had at least one adverse event, it will be regarded as 'Yes'; otherwise, it will be 'No'.

The indicators in this part are mainly descriptive. Statistical analysis methods are the same as those in 7.1.

(2) 24-week revision rate, where revision is defined as any component removal for any reason.

Calculation principle: Based on the collected adverse events in the CRF, if the measure taken for the implant is filled as "Revision" and the difference between the date of occurrence of the event and the date of the operation is \leq 196 days, the revision is determined as "Yes"; if postoperative 24-week follow-up is failed, it is determined as "Missing"; others are determined as 'No';

The indicators in this part are mainly descriptive. Statistical analysis methods are the same as those in 7.1.

(3) 24-week re-operation rate, where re-operation is defined as secondary operation of the fracture site for any reason.

Calculation principle: According to the AEs in CRF. If AE "re-operation" site collected in the CRF and occurrence of the event and the date of the operation is \leq 196 days, it is determined as 'Yes'; if postoperative 24-week follow-up is failed, it is determined as 'Missing'; others are determined as 'No'.

The indicators in this part are mainly descriptive. Statistical analysis methods are the same as those in 7.1.

- (4) Clinical outcomes
- ➤ SF-12
- Harris Hip Score
- ► EQ-5D

Calculation principle for SF-12 Score:

SF-12 v2 Questionnaire (each item consists of 8 parts: body functions, physical conditions, body pain, general health, mental health, emotional conditions, social functions and vitality) and general physical and mental health assessment.

Calculation principle: SF-12 scores will be calculated by special software, and statistical analysis will be performed using "_NBS" variable.

The indicators in this part are mainly descriptive. The descriptive analysis results of the SF-12 score and the change from baseline at each follow-up will be given. The statistical analysis method is the same as 7.1. At the same time, the 95% confidence interval of the mean value of change value from each group, the

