7.7 Concomitant medication, adverse events (AEs) or serious adverse events

(SAEs)

For concomitant medication, the subject's concomitant medication is provided in the form of a list.

The AEs and investigational device-related AEs in subjects will be tabulated and summarized, respectively. The list of subjects reported with AEs/ investigational device-related AEs includes site number, random number, group, age, gender, name of AE (SOC code), name of AE (PT code), time of postoperative occurrence (day), remission time (day), severity, measures taken, outcome, correlation with surgery, correlation with investigational device, withdrawal from the trial due to AEs, whether it is unanticipated adverse device effect (UADE), device failure or SAE.

Investigational device-related AEs refer to those "definitely related", "probably related" and "possibly related" with the investigational device;

Time of postoperative occurrence (day) = Date of occurrence of AE - Date of surgery,

Remission time (day) = End date of AE - Date of occurrence of AE.

The summary form will list the total number of cases of AEs/investigational device-related AEs, the total number of subjects suffering from AEs/investigational device-related AEs.

Wherein, the total case of AEs refers to the number of subjects suffering from AEs, and the AEs occur in the subject at least one time, which is considered as "Yes";

Statistical analysis of the severity of adverse events, the relationship with the study device and the relationship with the surgery was performed. If multiple adverse events occurred in a patient, the analysis was performed with the most severe or highest correlation.

The SAEs and investigational device-related SAEs in subjects will be tabulated and summarized, respectively; such data will be presented in the same form as AEs. The list of subjects reported with SAEs/investigational device-related SAEs includes site number, random number, group, age, gender, name of SAE (SOC code), name of SAE (PT code), time of postoperative occurrence (day), remission time (day), severity, outcome, correlation with surgery, correlation with investigational device and SAE.

The list and summary of UADEs in subjects will be presented respectively in the same form as AEs.

The calculation method of the time of postoperative occurrence (day) and remission time (day), the presentation of the summary form and the statistical principle are the same as those for AEs.

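### Read in sentence order, the SAP's 24-week revision and reoperation rules keep events from subjects lost to follow-up but drop lost subjects without an event, which overstates both FAS rates if loss is largely unrelated to revision risk

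*SAP*

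**What the plan says.** SAP 7.4(2) defines revision from the adverse events collected in the CRF. A subject is Yes if the measure taken for the implant is a revision and "the difference between the date of occurrence of the event and the date of the operation is" no more than 196 days. Only after that test does the sentence deal with subjects who lack the week-24 follow-up: "if postoperative 24-week follow-up is failed, it is determined as" Missing. SAP 7.4(3) applies the same order to reoperation: "if postoperative 24-week follow-up is failed, it is determined as 'Missing'; others are determined as 'No".

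Three other places settle what happens next:

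- SAP 6.5, on endpoints other than the primary: "Other missing indicators will not be carried forward and will be directly analyzed based on the actually observed data". Missing subjects therefore leave the denominator.
- SAP 6.3: "All baseline demographic data and secondary efficacy indicator analysis will be performed on the basis of FAS". Safety uses the same set. Tables 35 and 36 show the two rates with the number analysed and the number missing.
- Protocol 8.5 treats revision as the end of study participation, so a revised subject may well have no 24-week visit and still be Yes.

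Two places point the other way. Protocol 9.2 says that subjects who discontinue early are included in the analysis. SAP 7.4(1), the adverse event rule directly above, has no Missing category: anyone without a recorded event is No.

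**The concern.** Having an event is one of the two ways into the denominator; the other is attending week 24. Subjects who are lost contribute if they had an event first and contribute nothing if they did not, so the event-free time they were observed is thrown away. That selects on the outcome and pushes each arm's rate up. The size of the push grows with the share lost, so unequal loss between arms creates a difference where none exists. These are the 24-week device-failure rates in a report intended for registration. The same revision would also be divided by the whole group in the adverse event summary (Table 80) and by a smaller number in Table 35.

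**Working it through.** **Plan's own figures.** With union 95% in both arms, margin 0.10, one-sided 0.025 and 80% power: n = (1.960 + 0.842)² × 2 × 0.95 × 0.05 / 0.10² = 74.6, so 75 per arm. Then 75/0.80 = 93.75, so 94 per arm and 188 in total. Both match SAP 6.2. The documents give no expected revision or reoperation rate for this trial. For illustration I use the reoperation rates in Protocol Table 4 (4.3% and 6.5%, the latter for PFNA-II).

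**Formula.** Let p be the true risk to day 196, d the share lost before week 24, and f the share of a lost subject's risk that falls before the loss. The value of f is assumed: 0 means all losses are immediate, about 0.5 means losses spread evenly, and 1 means all losses come at the end. With loss unrelated to risk, the expected rate under the rule is

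[(1−d)p + d·p·f] / [(1−d) + d·p·f].

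Worked case, p = 6.5%, d = 20%:

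- f = 0.5: (0.052 + 0.0065) / (0.80 + 0.0065) = 0.0585/0.8065 = 7.25%.
- f = 1: 0.065 / (0.80 + 0.013) = 0.065/0.813 = 8.00%.

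| True risk | Loss | f = 0 | f = 0.5 | f = 1 |
|---|---|---|---|---|
| 4.3% | 20% | 4.30% | 4.81% | 5.32% |
| 6.5% | 20% | 6.50% | 7.25% | 8.00% |
| 6.5% | 5% | 6.50% | 6.66% | 6.82% |

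At 20% loss, relative inflation is about 12% (f = 0.5) to 23–24% (f = 1). At 5% loss it is about 2.5% to 5%.

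**Simulation.** Two million subjects were simulated with constant hazard and 20% loss at uniform times. The true risk was 6.53%. Kaplan-Meier gave 6.53%, the SAP rule 7.30%, and events over all subjects 5.89%.

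**Unequal loss.** Assume 10% versus 25% loss and the same true risk of 6/94 = 6.383% in both arms.

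- f = 0.5: (0.95 × 0.06383)/(0.90 + 0.05 × 0.06383) = 6.714%, against (0.875 × 0.06383)/(0.75 + 0.125 × 0.06383) = 7.368%. The gap is 0.65 points.
- f = 1: 0.06383/0.90638 = 7.042%, against 0.06383/0.76596 = 8.333%. The gap is 1.3 points.

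**If the priority were reversed.** Take 94 subjects, 4 events and 19 event-free losses. The rule in sentence order gives 4/75 = 5.33%. If Missing overrode Yes and two of the four had no visit, the result would be 2/73 = 2.74%.

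**The case against.** The strongest reply is that these endpoints are labelled mainly descriptive, no success criterion uses them, and Tables 35 and 36 print the event count and the number missing, so a reader can compute events over all FAS subjects. With 6 events in 94, one arm's standard error is √(0.0638 × 0.9362/94) = 2.5 points, larger than the bias. All of this stands and limits the importance. It does not make the printed rate right, and events over all subjects is not the answer either, because it ignores events after loss (5.89% against a true 6.53%).

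Four stronger readings are tempting, and the documents do not support them:

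- **That events on the SAE form would be missed, making the rates far too low.** Protocol 8.0 does mark the AE form "DO NOT COMPLETE" for a serious event, and the SAE listing in SAP 7.7 has no measures-taken item. But the AE listing in the same section (Table 79) carries both measures taken and a flag for SAE, and Protocol 8.0 calls both forms adverse event reporting. The CRFs are not among the documents.
- **That open-label conduct makes unequal loss likely.** Protocol 7.5 keeps patients blinded until they finish follow-up. The 10% versus 25% split is an illustration only.
- **That the rates are overstated whatever happens.** If lost subjects had three times the risk, mostly unseen (f = 0.25, 20% loss), the rule gives 7.63% against a true 9.10%. At f = 0 there is no bias.
- **That the full inflation of 94/75 = 1.25 is the expected size.** That takes events over 94 as the truth, which assumes no lost subject had a later event. It roughly doubles the likely size.

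**Conclusion.** The point holds for the FAS tables and should be corrected. At the planned attrition, the likely overstatement is about 0.8 points on a true risk of 6.5%, with an upper limit of 1.5 points. The false difference between arms is about 0.65 points, and about 1.3 at the extreme, under the assumed unequal loss. This rests on three conditions: loss is largely unrelated to revision risk, some risk time is observed before loss, and Yes is tested before Missing. The last follows from the order of the sentence; the SAP does not state it, and the opposite order would understate the rates, so the wording needs attention either way. The point does not extend to Tables 45 and 46, because the per-protocol set excludes subjects without a week-24 primary outcome whether or not they had an event. The non-inferiority conclusion on union does not depend on these rates.

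**What to change.** In SAP 7.4(2) and (3):

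- State that a recorded event within 196 days takes priority over missing follow-up.
- Estimate the 24-week (day 196) revision and reoperation rates in the FAS by Kaplan-Meier, or by cumulative incidence with death as a competing event, censoring event-free subjects at last contact. Name one of the two in advance. Protocol 1.1 cites first-year mortality of 11% to 30%, so some losses may be deaths, and the current rule codes an event-free death as Missing.
- Report the rate per arm and the difference with its 95% confidence interval, with the number at risk. The 24-week visit may fall anywhere from day 140 to day 196, so numbers thin toward the end.
- Show events over all FAS subjects alongside as a lower reference.

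The cost is a change of SAP wording and a few lines of code; event and surgery dates are already used in the rule. With few events, the intervals will be wide.

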5.2. Secondary Endpoints

The following secondary endpoints will be evaluated:

- Adverse events (type and frequency) for all adverse events will be compared for the investigational and control groups
- 24-week revision rate where revision is defined as removal of any component for any reason.
- 24-week reoperation rate is defined as secondary surgery at the fracture site(s) for any reason
- Clinical Outcomes
 - o SF-12
 - Harris Hip Score
 - o EQ-5D
- Radiographs: incidence of complications such as loosening or cut-out that require reoperation or revision

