6.2 Sample size calculation

The sample size calculation is determined based on the primary endpoint using PROC POWER in SAS software version 9.3. It assumes that the fracture union rate at 24 weeks after surgery in the TFNA group would be equivalent to that of the PFNA-II group, and a common fracture union rate is approximately 95% or greater based on the literature review. With a non-inferiority margin of 0.10 and a power of 80%, this implies a sample size of 75 for the TFNA and of 75 for PFNA-II surgery groups, respectively. The sample size will be increased to 188 (94 per group) to accommodate potential 20% attrition.

The sample size applies to patients enrolled, randomized, and actually treated. Some patients who enroll in a study and are randomized may not be ultimately treated for various reasons. Patient enrollment and randomization will continue until the proposed sample size for treated patients is complete.

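### In the FAS, the 24-week revision and reoperation rates keep events in early leavers but drop event-free early leavers, so both are biased upward by an amount that depends on each arm's dropout

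*SAP*

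**What the plan says.** Protocol 5.2 lists as secondary endpoints the "24-week revision rate where revision is defined as removal of any component for any reason" and a reoperation rate. SAP 7.4(3) words the latter as "24-week re-operation rate, where re-operation is defined as secondary operation of the fracture site for any reason".

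SAP 7.4(2) and (3) use the same three-step coding:

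1. *Yes* if the event is recorded no more than 196 days after surgery. A completed 24-week visit is not required.
2. Then, "if postoperative 24-week follow-up is failed, it is determined as" *Missing*.
3. *No* for all others.

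SAP 6.5 says of endpoints other than the primary: "Other missing indicators will not be carried forward and will be directly analyzed based on the actually observed data". A *Missing* subject therefore leaves the denominator. SAP 6.3 places the secondary and safety analyses in the FAS, which keeps implanted subjects who leave early.

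Three other places bear on the point:

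- SAP 7.4(1) codes adverse events differently: "if the subject has had at least one adverse event, it will be regarded as" *Yes*, and otherwise *No*. Event-free leavers stay in that denominator.
- Protocol 9.2 says that subjects who discontinue early are to be part of the analysis.
- SAP 6.2 plans for early loss: "The sample size will be increased to 188 (94 per group) to accommodate potential 20% attrition".

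**The concern.** Four records show how the rule works in the FAS:

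| Record | Code |
|---|---|
| Revised on day 60, then withdrew | *Yes* |
| Event-free, lost on day 120 | *Missing* |
| Event-free, died on day 150 | *Missing* |
| Event-free completer | *No* |

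An early leaver's follow-up is used if it contains an event and discarded if it does not. Leaving can only remove non-events, so the rate is pushed up, and pushed further in the arm that loses more subjects.

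Revision and reoperation are the secondary endpoints closest to device failure. Tables 35 and 36 compare the arms with a P value. Unequal dropout could therefore show up as a difference between devices when there is none.

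**Working it through.** **The plan's attrition figure.** SAP 6.2 takes "a common fracture union rate is approximately 95% or greater based on the literature review". With a margin of 0.10, one-sided alpha of 0.025 and 80% power, (1.960 + 0.842)² × 2 × 0.95 × 0.05 / 0.10² = 74.6, so 75 per arm. Then 75 / 0.80 = 93.75, so 94 per arm and 188 in total. The plan's figures reproduce, and 20% is the loss it allows for.

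**Inputs for the rule**

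- p, the true 24-week risk: 6.5%. This is the PFNA-II reoperation figure in Protocol Table 4 and is illustrative only. The documents assume no 24-week revision or reoperation rate.
- d, the share failing the 24-week visit: 20%, assumed equal to the planned attrition.
- f, the share of leavers' events recorded before they leave. The documents do not give it, so it runs from 0 to 1.
- Dropout is assumed independent of events.

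**Formula.** Recorded events are p[(1−d) + d·f]. Event-free completers are (1−d)(1−p). The reported rate is events / (events + event-free completers):

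rate = p[(1−d) + d·f] / [(1−d) + d·f·p]

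**Results at p = 6.5%, d = 20%**

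| f | Calculation | Rate | Relative excess |
|---|---|---|---|
| 0 (all leave before any event) | 0.052 / 0.800 | 6.50% | 0% |
| 0.5 (even timing) | 0.0585 / 0.8065 | 7.25% | 11.6% |
| 1 (all leave late) | 0.065 / 0.813 | 8.00% | 23.0% |

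The ceiling at d = 20%, for rare events and late leaving, is 1/0.80 = 1.25, or just under 25%. If only 10% fail the visit, the excess is 5.2% (f = 0.5) to 10.3% (f = 1).

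**Simulation check.** Over 196 days with independent dropout, even timing of both events and dropout gave 11.9% and late dropout gave 23%. When everyone who left did so on day 14 and events were spread evenly, the excess was only 1.9%. In a separate set of 6,000 simulated trials of 94 per arm followed to day 168, the rule gave 7.27% with even timing and 7.61% with early events. Kaplan-Meier on the same data gave 6.52% and 6.46%. No deaths were simulated. Without deaths, cumulative incidence and one minus Kaplan-Meier coincide.

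**Dependence on arm.** Take a true risk of 6.5% in both arms and late leaving (f = 1). With 10% dropout the rate is 0.065 / 0.9065 = 7.17%. With 25% it is 0.065 / 0.76625 = 8.48%. The false difference is 1.3 points.

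**Scale.** The excess is 0 to 1.5 points. The per-arm standard error is √(0.065 × 0.935 / 94) = 2.5 points, or 2.8 points with 75 subjects. About 94 × 0.065 = 6 events per arm would be expected.

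**The case against.** **The headline range is conditional.** A reader might infer that 20% attrition by itself makes both rates 12 to 23% too high. The documents do not support that. The 20% is a sample-size allowance for the primary endpoint, not a forecast of failed visits. Nothing is said about when subjects leave or when events occur, and no revision rate is given. The range at 20% is 0% to just under 25%. This part of the objection stands.

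**Not every table is affected.** A reader might extend the point to PPS Tables 45 and 46. SAP 6.4 removes subjects without a 24-week union outcome from the PPS whether or not they had an event, so the mechanism largely does not operate there. Protocol 10.10.6 also puts secondary efficacy in the per-protocol set. This stands, but the SAP still plans the FAS tables.

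**The effect is small and visible.** SAP 7.4 calls these endpoints mainly descriptive, no success criterion rests on them, and the tables print the number missing by arm. The 1.3-point false difference is about a third of the standard error of the difference (2.54 × √2 = 3.6 points). All true, and it limits the weight of the point. It does not make the rule unbiased.

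**Coding an unobserved 24-week status as missing is consistent with SAP 6.5.** It would be if applied to all leavers. Here it applies only to those without an event. The contrast with item (1) is weaker than it looks, because that item has no fixed horizon.

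**The order of precedence is not stated.** If *Missing* overrode *Yes*, the bias would not be upward. But Protocol 8.5 lists revision among the events that end participation, so that reading could delete the very events the revision rate is meant to count. Either reading needs a rewrite.

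**Mortality.** The 11 to 30% in Protocol 1.1 is first-year mortality and should not be applied directly to 24 weeks in this restricted population.

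**Conclusion.** The concern holds for the FAS analysis in Tables 35 and 36. In written order, the rule treats leavers with and without an event asymmetrically, biases both rates upward, and ties them to each arm's dropout. It also sits badly with Protocol 9.2.

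If 20% fail the visit, the true risk is 6.5% and dropout is independent of events, the excess is 0 to 1.5 percentage points (0 to 23% relative; about 12% with even timing). Equal true risks with 10% and 25% late dropout would give a false difference of about 1.3 points. These figures illustrate the mechanism and do not predict this trial's result.

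A reader might also infer that the non-inferiority claim is at risk. It is not, because the primary endpoint does not use this coding. The point is a correction to two secondary device-failure endpoints, worth making before analysis.

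**What to change.** In SAP 7.4(2) and (3) and in Tables 35 and 36:

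- Delete the *Missing* code.
- Estimate the 24-week cumulative incidence of first revision and of first reoperation in the FAS, from time to first event.
- Censor event-free subjects at their last recorded visit or contact, and treat death as a competing event.
- Give the between-arm difference with a 95% confidence interval.
- State one time horizon. The SAP counts events to day 196, while the endpoint is named for 24 weeks (day 168). The choice decides whether events on days 169 to 196 count.

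The cost is SAP wording and one standard survival procedure. Event and surgery dates are already used by the rule. The sponsor should confirm that the date of last visit or contact and the date of death are recorded, since the CRF is not among the documents. The downside is that the rates become slightly less simple to describe.
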